#### **7.1.2.10 End of Part 3 (Visit 3.5: Week 40/ End of Study for Part 2a; Week 32/End of Study for Part 2b; $\pm 1$ Week)**

- A full physical examination including vital signs, weight and height will be carried out.
- 12-lead ECG will be performed.
- Blood samples will be taken for biochemistry, hematology, and biochemical bone markers.
- All females will undergo a serum pregnancy test.
- All AEs and concomitant medication will be recorded.
- Confirmation of dialysis adequacy and dietary advice will be made.
- The primary reason for withdrawal will be recorded, if applicable.
- All returned study medication will be counted and recorded, and compliance calculated.
- An End of Study (EOS) Visit should be performed for all subjects in the study, including those subjects who discontinue early.

#### **7.1.3 Follow-up Period**

The safety follow-up call for this protocol is 7-14 days following last dose of investigational product ([Table 1](#) and [Table 3](#)). Subjects who discontinue due to kidney transplantation, will have their safety follow-up call after  $30 \pm 7$  days from the last dose.

The telephone call is initiated by the site staff to query for serious adverse events (SAEs), AEs, and concomitant treatments.

#### **7.1.4 Additional Care of Subjects After the Study**

Not Applicable.

### **7.2 Study Evaluations and Procedures**

#### **7.2.1 Demographic and Other Baseline Characteristics**

Patient demographic details, medical history, vital signs, including height, weight, physical examination, biochemistry, hematology, serum pregnancy test, type of dialysis (hemodialysis or peritoneal), vitamin D levels, and concomitant medication data will be obtained at Visit 1.0 (Part 1, [Table 1](#) or Part 2b and 3, [Table 3](#)) or Visit 2.0 (Part 2a and 3, [Table 1](#)).

#### **7.2.2 Efficacy**

The primary efficacy endpoint is the percentage of subjects achieving age-specific KDOQI targets for serum phosphate level following 8 weeks of treatment with lanthanum carbonate.

The KDOQI serum phosphate targets are defined as:

- Adolescents aged  $\geq 12$ -18 years:  $\leq 5.5$ mg/dL (1.78mmol/L)
- Children aged 10 years to  $< 12$  years:  $\leq 6.0$ mg/dL (1.94mmol/L)

The secondary efficacy endpoints will be evaluated by analysis of, phosphorus PTH, ALP, bone ALP, osteocalcin, TRAP, FGF-23, sclerostin and fetuin-A taken from blood samples at Visits 2.0, 2.4, 2.8 and 3.5 for Part 2a (see [Table 1](#)) and at Visits 1.0, 2.4, and 3.5 for Part 2b (see [Table 3](#)).

### **7.2.3 Safety**

#### **7.2.3.1 Medical and Medication History**

Medical and renal history will be recorded.

#### **7.2.3.2 Physical Examination**

Abnormalities identified at Visit 1.0 (see [Table 1](#) and [Table 3](#)) or Visit 2.0 (see [Table 1](#)), will be documented in the subject's source documents and on the medical history CRF. Changes after these visits will be captured as AEs on the AE CRF page, as deemed by the Investigator.

#### **7.2.3.3 Adverse Event Collection**

At each study visit, subjects will be questioned in a general way to ascertain if AEs have occurred since the previous visit (eg, "Have you had any health problems since your last visit?"). Adverse events are collected from the time informed consent is signed.

#### **7.2.3.4 Vital Signs**

Blood pressure should be determined by cuff (using the same method, the same arm, and in the same position throughout the study). Any clinically significant deviations from baseline vital signs which are deemed clinically significant in the opinion of the Investigator are recorded as an AE.

Height and weight will be measured as part of the vital signs assessments.

#### **7.2.3.5 Clinical Laboratory Evaluations**

The name and address of the each clinical laboratory used in this study will be maintained in the Investigator's files at each site.

All clinical laboratory assays will be performed according to the laboratory's normal procedures. Reference ranges are supplied by the laboratory and used to assess the clinical laboratory data for clinical significance and out-of-range pathological changes. The Investigator should assess out-of-range clinical laboratory values for clinical significance, indicating if the value(s) is/are not clinically significant or clinically significant. Abnormal clinical laboratory values, which are unexpected or not explained by the subject's clinical condition may be, at the discretion of the Investigator or Sponsor, repeated until confirmed, explained, or resolved as soon as possible.

The following clinical laboratory assessments will be performed:

### Biochemistry

Blood samples (approximately 4.0mL) for biochemistry will be taken according to the Schedule of Assessments (see [Table 1](#) and [Table 3](#)). The following parameters will be assessed:

Sodium	Aspartate aminotransferase (AST)
Potassium	Alanine aminotransferase (ALT)
Calcium	Alkaline phosphatase (ALP)
Urea	Gamma glutamyl transferase (GGT)
Creatinine	Total bilirubin
Albumin	Magnesium
Total protein	Serum phosphorus

25-hydroxy Vitamin Da,

a 25-hydroxy Vitamin D will be measured at baseline and EOS only

Changes from baseline will be recorded as an AE if clinically relevant.

### Hematology

Blood samples (approximately 500µL) for hematology will be taken according to the Schedule of Assessments (see [Table 1](#) and [Table 3](#)). The following parameters will be assessed:

Hemoglobin	Mean corpuscular hemoglobin (MCH)
Hematocrit	Mean corpuscular hemoglobin concentration (MCHC)
Red blood cells	White blood cell count – total and differential
Mean corpuscular volume (MCV)	Platelet count

Changes from baseline will be recorded as an AE if clinically relevant.

### Biochemical Bone Markers

Blood samples (approximately 3.0mL) for biochemical bone markers will be taken according to the Schedule of Assessments (see [Table 1](#) and [Table 3](#)). The following parameters will be assessed:

TRAP	FGF-23
Osteocalcin	Bone ALP
PTH a	Sclerostin
Fetuin- A	

Changes from baseline will be recorded as an AE if clinically relevant.

### 7.2.3.6 Pregnancy Test

A serum pregnancy test is performed on all female subjects at Visit 1.0, and/or Visit 2.0, and at the final visit (Visit 3.5), or if pregnancy is suspected, or on withdrawal of the subject from the study (see [Table 1](#) and [Table 3](#)).

### 7.2.3.7 Electrocardiogram

An ECG will be carried out at Visit 1.0, at Visits 2.0, 2.8 and 3.5/EOS for Part 2a (see [Table 1](#)), and at Visits 1.0, 2.4, and 3.5/EOS for Part 2b (see [Table 3](#)).

The ECG must be assessed by either a cardiac specialist or by a study physician who is trained to perform this assessment.

## 7.2.4 Others

### 7.2.4.1 Clinical Pharmacology Assessments

#### Blood Sampling for Lanthanum Pharmacokinetic Evaluation

Actual pharmacokinetic blood sample collection times relative to the time of dosing will be monitored. The Sponsor's expectation is that the Investigator will ensure that every effort is made to collect all pharmacokinetic blood samples at the precise protocol-scheduled time.

Blood samples (1mL each) for pharmacokinetic evaluation will be collected during all 3 study periods (Parts 1, 2 [2a and 2b], and 3).

Part 1. Blood samples for determination of single-dose lanthanum pharmacokinetics will be collected at pre-dose and at 3, 5, 6, 8, 12, 24, and 48 hours after dosing.

Part 2 (2a or 2b) and Part 3. Pharmacokinetics will be evaluated during lanthanum carbonate dosing using a sparse sampling approach. Blood samples (at least 2 per subject) for pharmacokinetic assessments will be collected during Parts 2 (2a or 2b) and 3 in defined time windows (to be selected from: 0-2 hours, 2-4 hours and 4-6 hours after the first dose/meal of the day, so as to cover the full dosing interval).

The actual time that the sample was taken will be recorded; it should be within  $\pm 5$  minutes of the nominal in the first 4 hours after taking the investigational product,  $\pm 15$  minutes up to 24 hours after taking the investigational product (Parts 1, 2, and 3), and within  $\pm 60$  minutes thereafter (Part 1 only).

Samples drawn outside these parameters will be considered a protocol deviation.

**7.2.4.2 Pharmacodynamic Assessments**

Not Applicable.

**7.2.4.3 Quality of Life Assessments**

Not Applicable.

**7.2.4.4 Health Outcomes Assessments**

Not Applicable.

**7.2.5 Volume of Blood to be Drawn From Each Subject**

**Table 5: Volume of Blood to be Drawn From Each Subject**

Assessment		Sample Volume (mL)	Number of Samples	Maximum Total Volume (mL)
Pharmacokinetic samples		1.0 a	12	12.0
Safety	Biochemistry with $\beta$ -HCG a	4.0	4	16.0
	Hematology	0.5	2	1.0
	Biochemical bone markers	3.0	4	12.0
	Centrally confirmed phosphate b	0.1-0.7 c	2	1.4
Total mL				42.4

HCG=human chorionic gonadotropin

a  $\beta$ -HCG testing for all female subjects will be analyzed from the biochemistry samples so no additional blood volume is required

b Only for those subjects who require confirmation of their phosphate levels from the central laboratory, during the washout periods

c Volume will vary according to country

In the originally proposed study, it was expected that approximately 41.0mL of blood will be taken from all subjects, regardless of sex; a maximum of 42.4mL of blood will be taken from those subjects who require confirmation of their phosphate levels during both washouts in Part 2 (41.7mL if they only require confirmation during 1 of the washouts).

Under Version 6.0 of the protocol, subjects will enter Part 2b, after screening at Visit 1.0/Week 0 for this part, for 8 weeks of lanthanum carbonate treatment only. They will undergo assessments for Part 2b and 3 as presented in [Table 3](#). It is expected that approximately 34mL of blood will be taken from all subjects, regardless of sex.

Note: The above amount of blood to be taken for each assessment is an estimate. The amount of blood to be taken may vary according to the instructions provided by the manufacturer or laboratory for an individual assessment. However, the total volume drawn over the course of the study should be approximately 41.0mL (maximum of 42.4mL). When more than 1 blood

assessment is to be done at the time point/period, if they require the same type of tube, the assessments may be combined.

## 8. ADVERSE AND SERIOUS ADVERSE EVENTS ASSESSMENT

### 8.1 Definition of Adverse Events, Period of Observation, Recording of Adverse Events

An *Adverse Event* (AE) is any untoward medical occurrence in a clinical investigation subject administered a pharmaceutical product and that does not necessarily have a causal relationship with this treatment. An AE can therefore be any unfavourable and unintended sign (including an abnormal laboratory finding), symptom, or disease temporally associated with the use of a medicinal (investigational) product, whether or not related to the medicinal (investigational) product (International Conference on Harmonisation [ICH] Guidance E2A 1995).

All AEs should be captured on the AE CRF.

All AEs are collected from the time the informed consent is signed until the defined follow-up period stated in Section 7.1.3 and are to be recorded on the appropriate AE pages in the CRF and in source documents. Where possible, a diagnosis, rather than a list of symptoms, should be recorded. If a diagnosis has not been made, then each symptom should be listed individually. In addition to untoward AEs, unexpected benefits outside the investigational product indication should also be captured on the AE CRF.

All AEs must be followed to closure (the subject's health has returned to his/her baseline status or all variables have returned to normal), an outcome is reached, stabilization (the Investigator does not expect any further improvement or worsening of the event), or the event is otherwise explained regardless of whether the subject is still participating in the study. When appropriate, medical tests and examinations are performed so that resolution of event(s) can be documented.

#### 8.1.1 Severity Categorization

The severity of AEs must be recorded during the course of the event including the start and stop dates for each change in severity. An event that changes in severity should be captured as a new event. Worsening of pre-treatment events, after initiation of investigational product, must be recorded as new AEs (for example, if a subject experiences mild intermittent dyspepsia prior to dosing of investigational product, but the dyspepsia becomes severe and more frequent after first dose of investigational product has been administered, a new AE of severe dyspepsia [with the appropriate date of onset] is recorded on the appropriate CRF).

The medical assessment of severity is determined by using the following definitions:

**Mild:** A type of AE that is usually transient and may require only minimal treatment or therapeutic intervention. The event does not generally interfere with usual activities of daily living.

**Moderate:** A type of AE that is usually alleviated with specific therapeutic intervention. The event interferes with usual activities of daily living, causing discomfort but poses no significant or permanent risk of harm to the research subject.

**Severe:** A type of AE that interrupts usual activities of daily living, or significantly affects clinical status, or may require intensive therapeutic intervention.

### 8.1.2 Relationship Categorization

A Physician/Investigator must make the assessment of relationship to investigational product for each AE. The Investigator should decide whether, in his or her medical judgment, there is a reasonable possibility that the event may have been caused by the investigational product. If there is no valid reason for suggesting a relationship, then the AE should be classified as ‘not related’. Otherwise, if there is any valid reason, even if undetermined or untested, for suspecting a possible cause-and-effect relationship between the investigational product and the occurrence of the AE, then the AE should be considered ‘related’. The causality assessment must be documented in the source document.

The following additional guidance may be helpful:

Term	Relationship	Definition
Related	Yes	The temporal relationship between the event and the administration of the investigational product is compelling and/or follows a known or suspected response pattern to that product, and the event cannot be explained by the subject’s medical condition, other therapies, or accident.
Not Related	No	The event can be readily explained by other factors such as the subject’s underlying medical condition, concomitant therapy, or accident and no plausible temporal or biologic relationship exists between the investigational product and the event.

### 8.1.3 Outcome Categorization

The outcome of AEs must be recorded during the course of the study on the CRF. Outcomes are as follows:

- Fatal
- Not Recovered/Not Resolved
- Recovered/Resolved
- Recovered/Resolved With Sequelae
- Recovering/Resolving
- Unknown

### 8.1.4 Symptoms of the Disease Under Study

Symptoms of the disease under study should not be classed as AEs as long as they are within the normal day-to-day fluctuation or expected progression of the disease. However, significant worsening of the symptoms should be recorded as an AE.

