## 1. BACKGROUND INFORMATION

### 1.1 Condition Background and Current Treatment

#### Chronic kidney disease

Lanthanum carbonate has been developed as a phosphate-binding agent for the treatment of hyperphosphatemia associated with chronic kidney disease (CKD). Control of serum phosphate levels is fundamental in the management of CKD, which leads to progressive decline in the kidney's ability to excrete phosphate, produce active vitamin D (calcitriol), and maintain calcium homeostasis.

CKD is associated with complex metabolic, bone and vasculature abnormalities that together encompass a syndrome defined in 2006 as CKD-mineral and bone disorder ([Moe et al. 2006](#)). Hyperphosphatemia and secondary hyperparathyroidism are implicated as central components in CKD- mineral and bone disorder.

The pathophysiological consequences of positive phosphate balance and hyperphosphatemia include hyperparathyroidism and the associated renal osteodystrophy. Hyperphosphatemia and hyperparathyroidism in CKD is a vicious cycle with serious consequences. The associated high turnover bone disease manifests with bone pain, bone fracture, bone deformity, osteopenia, myopathy, arthritis, resistance to erythropoietin due to marrow fibrosis, growth failure in children, and extraskeletal calcification.

Serum phosphorus levels vary depending on age ([Kidney Disease Outcomes Quality Initiative \[KDOQI\] Guideline 4, 2005](#)).

A limited number of clinical studies have been conducted in the pediatric population with phosphate binders ([Pieper et al. 2006](#); [Alon et al. 1986](#); [Clark et al. 1989](#); [Mahdavi et al. 2003](#); [Salusky et al. 2005](#)). Currently the only such products with an approved indication in children are calcium-based binders and aluminium hydroxide.

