### 8.2.4 Serious Adverse Event Collection Timeframe

All SAEs (regardless of relationship to study) are collected from the time the subject signs informed consent until the defined follow-up period stated in Section 7.1.3, and must be reported to the Shire Pharmacovigilance Department within 24 hours of the first awareness of the event.

In addition, any SAE(s) considered “related” to the investigational product and discovered by the Investigator at any interval after the study has completed must be reported to the Shire Pharmacovigilance Department within 24 hours of the first awareness of the event.

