#### Parts 2 and 3 (Efficacy – Percentage of Subjects Achieving KDOQI Target for Serum Phosphorus)

Originally, the sample size of at least 50 subjects for the PP set had been chosen based on practical considerations and on agreement with the Paediatric Committee of the European Medicines Agency. In order to obtain a PP Set of 50 subjects, a sample size of approximately 72 subjects were to be enrolled in Part 2. This assumed 70% of the subjects are eligible for the PP Set. This sample size has 81% power to show that the lower limit of the 95% confidence interval for the difference (LC – CC) in the percentage of subjects achieving serum phosphorus target is above the non-inferiority margin of -18%.

However, given the extreme difficulty in recruiting enough subjects to obtain at least 50 subjects for the PP set for the assessment of non-inferiority, serious consideration had to be given to adjust the sample size and focus of the study to safety, in order to complete it. The sample size has been adjusted to include at least 35 subjects, who complete 8 weeks of treatment with lanthanum carbonate and are assessable for the primary endpoint. This study is still useful in collecting information, where there is a void, regarding the use of lanthanum in the pediatric population.

For the investigation of safety profile in hyperphosphatemic children and adolescents with CKD on dialysis treated with lanthanum carbonate, a sample size of 35 subjects is necessary in order to observe at least one event with a true event rate of 5% at a probability of 83.4%.

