### 11.1 Adverse Events

Onset day of an AE is calculated as (start date of the AE - date of the first dose of IP) + 1. AEs will be classified into system organ class (SOC) and preferred term (PT) using Version 16.1, of MedDRA, to be determined closer to the conclusion of data collection.

An AE that occurs during the study will be considered a treatment emergent AE (TEAE) if it has a start date on or after the first dose of IP. TEAEs will be allocated to Part 1, Part 2, or Part 3, based on the onset date of the AE relative to the date and Part of the most recently administered IP. If an AE occurred more than 3 weeks after the date of the most recent IP, it will not be considered a TEAE. In the case of increases in severity, if there is more than 1 reference AE with the same preferred term then the AE with the greatest severity will be used as the benchmark for comparison to the AEs occurring in each Part of the study.

**Part 1:** An overall summary (**Table 4.2.1.1**) and summary by age group (**Table 4.2.1.2**) of the number of subjects in Safety Analysis Set 1 with TEAEs in Part 1 will be presented, including the number and proportion of subjects with any TEAEs, serious TEAEs, TEAEs related to lanthanum carbonate, TEAEs leading to study withdrawal, and TEAEs leading to death. The number of events, incidence, and percentage of TEAEs will be presented by SOC, and by preferred term (**Table 4.2.2.1**); by SOC, preferred term, and maximum severity (**Table 4.3.1.1**); and by SOC, preferred term, and relationship to lanthanum carbonate (**Table 4.3.2.1**). Similar summaries by SOC and preferred term will be produced for SAEs (**Table 4.4.1.1**), for deaths (**Table 4.4.2.1**), and for TEAEs leading to study withdrawal (**Table 4.4.3.1**). AEs (**Listing 7.1**), SAEs (**Listing 7.2**), AEs related to lanthanum carbonate (**Listing 7.3**), AEs leading to study withdrawal (**Listing 7.4**), and deaths (**Listing 7.5**) will be listed. AEs related to bone disease (preferred terms: adynamic bone disease and long bone fracture) are of special interest and will be summarised by SOC and preferred term (**Tables 4.5.1.1 and 4.5.2.1**) and listed separately (**Listing 7.6**).

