**Part 2:** An overall summary (**Table 4.2.1.3**) and summary by age group (**Table 4.2.1.4**) of the number of subjects in Safety Analysis Set 2 with TEAEs in Part 2 will be presented, including the number and proportion of subjects with any TEAEs, serious TEAEs, TEAEs related to IP, TEAEs leading to study withdrawal, and TEAEs leading to death. The number of events, incidence, and percentage of TEAEs in each treatment group will be presented by SOC and preferred term (**Table 4.2.2.2**); by SOC, preferred term, and maximum severity (**Table 4.3.1.2**); and by SOC, preferred term, and relationship to IP (**Table 4.3.2.2**). Similar summaries by SOC and preferred term will be produced for SAEs (**Table 4.4.1.2**), for deaths (**Table 4.4.2.2**), and for

TEAEs leading to study withdrawal (**Table 4.4.3.2**). AEs, AEs related to IP, SAEs, AEs leading to study withdrawal, and deaths will be listed (**Listing 7.1, Listing 7.3, Listing 7.4 and Listing 7.5**). TEAEs related to bone disease (preferred terms: adynamic bone disease and long bone fracture) are of special interest and will be summarised by SOC and preferred term for Part 2 (**Tables 4.5.1.2 and 4.5.2.2**) and listed separately (**Listing 7.6**).

**Part 2 and 3 combined (lanthanum carbonate only):** An overall summary (**Tables 4.2.1.5 and 4.2.1.7**) and summary by age group (**Tables 4.2.1.6 and 4.2.1.8**) of the number of subjects in Safety Analysis Set 2 and SCS with TEAEs in Part 2 and 3 combined will be presented. The number of events, incidence, and percentage of TEAEs will be presented by SOC by preferred term (**Tables 4.2.2.3 and 4.2.2.4**); by SOC, preferred term, and maximum severity (**Tables 4.3.1.3 and 4.3.1.4**); and by SOC, preferred term, and relationship to lanthanum carbonate (**Tables 4.3.2.3 and 4.3.2.4**). Similar summaries by SOC and preferred term will be produced for SAEs (**Tables 4.4.1.3 and 4.4.1.4**), for deaths (**Tables 4.4.2.3 and 4.4.2.4**), and for TEAEs leading to study withdrawal (**Tables 4.4.3.3 and 4.4.3.4**). AEs, AEs related to lanthanum carbonate, SAEs, AEs leading to study withdrawal, and deaths will be listed (refer to listings noted above). TEAEs related to bone disease (preferred terms: adynamic bone disease and long bone fracture) are of special interest and will be presented by SOC and preferred term in **Table 4.5.1.3 and Table 4.5.1.4** and by sex and age group in **Table 4.5.2.3 and 4.5.2.4** and will be listed separately. (**Listing 7.6**)

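### Protocol 8.1.4 leaves it to the investigator whether a non-serious bone event is expected progression, so such an event could miss the SAP's special-interest tables

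*Protocol*

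**What the plan says.** - **The exemption.** Under Protocol section 8.1.4, disease symptoms "should not be classed as AEs as long as they are within the normal day-to-day fluctuation or expected progression of the disease". The next sentence limits this: "However, significant worsening of the symptoms should be recorded as an AE". Neither expected progression nor significant worsening is defined.
- **The disease.** Protocol section 1.1, under chronic kidney disease, states: "The associated high turnover bone disease manifests with bone pain, bone fracture, bone deformity, osteopenia, myopathy, arthritis". Fracture is named. Adynamic bone disease is not.
- **The events of interest.** SAP section 11.1 says for Part 1: "AEs related to bone disease (preferred terms: adynamic bone disease and long bone fracture) are of special interest". For Part 2, and for Parts 2 and 3 combined: "TEAEs related to bone disease (preferred terms: adynamic bone disease and long bone fracture) are of special interest". These are the only events of special interest in the SAP. Tables 4.5.1.1 to 4.5.1.4, Tables 4.5.2.1 to 4.5.2.4 and Listing 7.6 report them, and all draw on recorded adverse events. The protocol does not mention events of special interest.
- **General capture.** Protocol section 8.1: "All AEs should be captured on the AE CRF". Section 8.2.4: "All SAEs (regardless of relationship to study) are collected from the time the subject signs informed consent".
- **Safety sample size.** Protocol section 9.13 says "a sample size of 35 subjects is necessary in order to observe at least one event with a true event rate of 5" per cent, with probability 83.4%. SAP section 2.5 gives 80.6% for 32 subjects, a change of number that SAP section 17 declares.

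**The concern.** Investigators decide what goes on the adverse event page from the protocol, not from the SAP. The protocol lets them leave off disease symptoms that follow the expected course, tells them that fracture is something this disease does, and never tells them that bone events are of special interest. One site could record a minor fracture as significant worsening and another could leave it off as expected CKD bone disease, and both would have followed the text. Up to 36 sites are planned.

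Amendment 5 moved the focus of the study to safety, and the safety profile is secondary objective 1. Part 2b has no comparator and there is no Data Monitoring Committee. Any omission under 8.1.4 can only lower the bone event count, and nothing in the special-interest tables would show that it had happened.

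**Working it through.** **Step 1. Follow a bone event through the recording rules.**

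| Route | Protocol section | Serious bone event | Non-serious bone event judged expected progression |
|---|---|---|---|
| SAE collection | 8.2.3, 8.2.4 | Captured; the SAE definition has no disease-progression exemption | Not applicable |
| Significant worsening | 8.1.4 | Not needed | Recorded only if the investigator sees significant worsening |
| Worsening of a pre-treatment event | 8.1.1 | Not needed | Does not address a first fracture |
| Physical examination change | 7.2.3.2 | Not needed | At the investigator's discretion; for Part 2b, examinations are scheduled only at Visit 1.0 and Visit 3.5/End of Study (Table 3) |
| Bone marker change | 7.2.3.5 | Not needed | Recorded if clinically relevant; markers do not count fractures |

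Neither schedule of assessments includes bone imaging. For a non-serious fracture, the adverse event page is in effect the only way into Tables 4.5.x and Listing 7.6, and 8.1.4 stands in front of it. No text exempts the two special-interest terms from 8.1.4.

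**Step 2. Reproduce the plan's own figures.** With true rate p = 0.05, P(at least one event) = 1 − (1 − p)^n.

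- n = 35 (Protocol 9.13): 1 − 0.95^35 = 0.834, as stated.
- n = 32 (SAP 2.5): 1 − 0.95^32 = 0.806, as stated.

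**Step 3. Illustrate non-recording.** Suppose a share c of events with a 5% true rate is recorded. Then P(at least one recorded) = 1 − (1 − 0.05c)^n. The documents give no value for c and no bone event rate, so both are assumptions. The last column takes all of the approximately 65 subjects who may be enrolled as exposed to lanthanum, an upper bound for Safety Analysis Set 2.

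| Share recorded, c | n = 35 | n = 32 | n = 65 (upper bound) |
|---|---|---|---|
| 1.00 | 83.4% | 80.6% | 96.4% |
| 0.90 | 80.0% | 77.1% | 95.0% |
| 0.75 | 73.8% | 70.6% | 91.7% |
| 0.50 | 58.8% | 55.5% | 80.7% |
| 0.25 | 35.6% | 33.1% | 55.8% |

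For example, c = 0.5 and n = 35 gives 1 − 0.975^35 = 0.588. The table shows how sensitive the calculation is. It does not estimate what happened at sites.

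**The case against.** The strongest reply is that the protocol, read as a whole, points towards recording.

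- Section 8.1.4 speaks of symptoms, and a new long bone fracture is a discrete event that most investigators would call significant worsening.
- Section 8.1.2 classes an event explained by the underlying condition as not related, which presupposes that such events are on the adverse event page.
- Serious fractures have their own route through the SAE rules.
- Section 1.1 names fracture but not adynamic bone disease, so it covers one of the two special-interest terms.
- Bone markers and height are scheduled secondary variables and do not depend on 8.1.4.
- The 5% rate in Protocol 9.13 and SAP 2.5 is for a generic event. The figures 35 and 32 are minimum numbers of 8-week completers, whereas the bone tables also use Safety Analysis Set 2, which does not require completion.
- The CRF completion guidelines, which may already deal with this, are not among the documents.

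All of this stands, and it sets the limits of the point. A reader might infer that sites are told to leave fractures off the adverse event page, that the special-interest tables will miss bone events generally, or that the stated 83.4% and 80.6% are wrong. The documents support none of these. The worsening sentence and the SAE rules rule out the first two, and the percentages were never stated for bone events. What the reply does not remove is the discretion: two sites can treat the same non-serious event differently and both comply, and the protocol nowhere says which treatment the SAP needs.

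**Conclusion.** The point holds in a limited form. Non-serious fractures or bone disease findings that an investigator judges to be expected progression could be left out of Tables 4.5.x and Listing 7.6. The textual support is firm for fracture, which section 1.1 names, and weaker for adynamic bone disease, which it does not. The direction of any error is known, towards fewer recorded events. Its size is not: the documents give neither a recording rate nor a bone event rate, and nothing shows that any event has been missed. The stated 83.4% and 80.6% remain correct for a generic 5% event. This is a cheap improvement to a safety-focused study, not a defect that undermines its safety analysis.

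**What to change.** Add to Protocol section 8.1.4, and repeat in the CRF completion guidelines:

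> This exemption does not apply to the SAP's bone events of special interest (adynamic bone disease, long bone fracture); these are always recorded as AEs, with any role of the underlying disease handled in the relationship assessment (8.1.2).

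Then query sites once, before database lock, for any such events in already enrolled subjects that were not recorded under the present text of 8.1.4.

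The cost is one sentence in two documents and one round of site queries. The downside is a few more adverse events, some due to the underlying disease, which section 8.1.2 already allows to be classed as not related.
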